5.1 Imputation rules

5.1.1 Study treatment

Full dates for study treatment collected on the eCRF are required; therefore, no imputations will be made.

5.1.2 AE date imputation

The following algorithm should be used to estimate start dates for which only partial information is known:

- Missing day and month
 - If the year is the same as the year of first study treatment, then the day and month of the start date of treatment will be assigned to the missing fields.
 - If the year is prior to the year of first study treatment, then December 31 will be assigned to the missing fields.
 - If the year is after the year of first study treatment, then January 1 will be assigned to the missing fields.
- Missing month only
 - Treat day as missing and replace both month and day according to the above procedure.
- Missing day only
 - If the month and year are the same as the year and month of first study treatment, then the start date of treatment will be assigned to the missing day.
 - If the month and year are before the year and month of first study treatment, then the last day of the month will be assigned to the missing day.
 - If the month and year are after the year and month of first study treatment, then the first day of the month will be assigned to the missing day.

If the imputed start date result is after the stop date (and the stop date is complete), the imputed start date will be reset to the stop date.

The following algorithm should be used to estimate stop dates for which only partial information is known:

- Missing year
 - Date left missing.
 - Missing month
 - Impute 'December'.
- Missing day

•

- Impute 'last date of that month'.

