2.1.1 General definitions

Study treatment

Patients will receive either sacubitril/valsartan or enalapril during the first 8 weeks of the study. Study treatment will refer to either of these two drugs.

Baseline

For safety labs and biomarkers, baseline is defined as the last non-missing assessment collected <3 hours from the first dose of study treatment, including matching placebos. For patients not treated, baseline is defined as the last non-missing assessment prior to or on the date of randomization. BNP and NT-proBNP values will be based on clinical laboratory samples processed and assessed by the central laboratory.

For other assessments, including those for which assessment time is collected (ECGs, HF Signs and Symptoms, and pregnancy tests), baseline is defined as the last non-missing assessment prior to or on the start date of study treatment (randomization date for patients not treated), including matching placebos.

Date of first administration of study treatment

Double-blind phase: The date of first administration of study treatment in the double-blind phase is defined as the first date a dose of study treatment is administered and recorded on the Dose Administration (Visit 2) electronic case report form (eCRF).

Open-label phase: The date of first administration of study treatment in the open-label phase is defined as the first date a dose of sacubitril/valsartan is administered in the open-label phase and recorded on the Dose Administration (Visit 7) eCRF.

Pooled phase: The date of first administration of study treatment in the pooled phase is defined as the first date a dose of sacubitril/valsartan is administered either in the double-blind phase or open-label phase.

Date of last administration of study treatment

Double-blind phase: The date of last administration of study treatment in the double-blind phase is defined as the last date a dose of study treatment is administered in the double-blind phase and recorded on the Dose Administration (Visit 7) eCRF, or earlier if prematurely discontinued and recorded on the Early Investigational Product Permanent Discontinuation eCRF.

Open-label phase: The date of last administration of study treatment in the open-label phase is defined as the last date of sacubitril/valsartan is administered in the open-label phase and recorded on the Drug Administration eCRF.

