Pooled phase: The date of last administration of study treatment in the pooled phase is defined as the last date of sacubitril/valsartan administered either in double-blind phase or open-label phase.

Study day

The study day describes the day of the assessment relative to the date of randomization.

The study day will be calculated as the difference between the date of assessment and the date of randomization plus 1. If the date of assessment is prior to the date of randomization, the study day will be negative and will be calculated as the difference between the date of the assessment and the date of randomization.

Double-blind phase

Assessments performed at Weeks 1, 2, 4, 6, or 8 (including, but not limited to, vital signs) are assigned to the double-blind phase for summarization purposes. Unscheduled assessments are not assigned to a study phase for purposes of by-visit summaries.

For summarization of adverse events [AEs], medications, protocol deviations, notable vital signs and laboratory abnormalities, and symptomatic hypotension by study phase, an assessment during the double-blind phase is defined as any assessment obtained in the following time interval:

Date of randomization (or date of first administration of study treatment, as appropriate) through the date of the Week 8 visit, inclusive. For patients without a Week 8 visit, a projected Week 8 visit date will be derived relative to their randomization date.

An 'active treatment' assessment is defined for sensitivity analyses starting with the first dose of study treatment in patients randomized to enalapril and the third dose of study treatment in patients randomized to sacubitril/valsartan.

Open-label phase

Assessments performed at Weeks 10 or 12 (including, but not limited to, vital signs) are assigned to the open-label phase for summarization purposes. Unscheduled assessments are not assigned to a study phase for purposes of by-visit summaries.

For summarization of AEs, medications, protocol deviations, notable vital signs and laboratory abnormalities, and symptomatic hypotension by study phase, an assessment during the open-label phase is defined as any assessment obtained in the following time interval:

After the date of the Week 8 visit. For patients without a Week 8 visit, a projected Week 8 visit date will be derived relative to their randomization date.

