Patients who died, withdrew consent, or were lost to follow-up prior to or on their projected Week 8 visit date will be excluded from the open-label phase.

Pooled phase

An assessment during the pooled phase is defined as any assessment obtained in the doubleblind phase for patients randomized to sacubitril/valsartan, or any assessment obtained in the open-label phase regardless of randomized treatment arm.

Last contact

The date of last contact will be determined from the Date of Last Contact field on the Study Completion/Exit eCRF.

Year, month and week

For reporting purposes, the rules below will be followed to convert a year, month and week to days.

1 year = 365.25 days

1 month = 30.3475 days

1 week = 7 days

1 day = 24 hours

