2.4.1 Study treatment / compliance

The duration of double-blind study treatment phase is defined as:

Duration (days) = (date of last study treatment in double-blind study phase - date of first study treatment) +1

The first date of study treatment is recorded on the Dose Administration (Visit 2) eCRF.

The duration of the open-label study treatment phase is defined as:

Duration (days) = (date of last study treatment in open-label study phase - date of first study treatment in open-label phase) +1

The duration of the pooled phase (sacubitril/valsartan in double-blind phase and/or sacubitril/valsartan in open-label phase) is defined as:

Duration (days) = (date of last study treatment of sacubitril/valsartan [any phase] - date of first study treatment of sacubitril/valsartan [any phase]) +1

Summary statistics will be displayed for the duration of double-blind study treatment, duration of open-label study treatment and duration of pooled sacubitril/valsartan by phase.

The durations will also be categorized into weekly time intervals (<7 days, 7 - <14 days, 14 - <21 days, ..., etc.). The number and percentage of patients in each category will be presented by phase.

Total patient-days of exposure will also be summarized by phase.

In addition, the number and percentages of each dose level dispensed by visit will be summarized by treatment group and open-label sacubitril/valsartan. The number and percentage of the maximum dose levels dispensed will also be presented by treatment group and open-label sacubitril/valsartan. Similarly, the up-titrated doses, down-titrated doses and unchanged doses will be summarized by visit, treatment group and open-label sacubitril/valsartan. The number and percentage of patients who were dispensed dose level 3 by Week 6 will be summarized by treatment group.

An additional summary of patient dose level and titration data will be generated by visit and systolic blood pressure using the visit-specific systolic blood pressure cut-off values from the dose titration schedule.

All information on dose administration will be listed.

2.4.2 **Prior**, concomitant and post therapies

Non-HF Medications

Prior and concomitant non-HF medications will be coded according to the World Health Organization (WHO) Drug Reference List (v15.3 or later). Prior and concomitant medications are mutually exclusive, as defined below:

- Prior medications are defined as any medication with an end date prior to the first dose of study treatment

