2.8.1.2 General rules for AE reporting

AE summaries will include all treatment-emergent AEs (TEAEs). TEAEs are defined as AEs starting on or after the first day of study treatment. All AEs will be listed. AEs starting prior to the first day of study treatment (non-TEAEs) will be flagged in the listings.

All TEAEs will be summarized by study phase as defined in Section 2.1.1.

TEAEs will be summarized by presenting the number and percentage of patients having at least one TEAE, having at least one TEAE in each primary SOC, and for each PT using MedDRA coding. A patient with multiple occurrences of a TEAE will be counted only once in the AE category.

Separate summaries will be presented by SOC, PT and severity. A patient with multiple severities for an AE will be summarized under the worst severity recorded for the event.

Any information collected will be listed as appropriate.

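### Adverse events with a missing start day, recorded in the month of the Week 8 visit, always fall in the double-blind tables, even when they began in the open-label phase

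*SAP*

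**What the plan says.** **Imputation.** SAP 5.1.2 compares a partial AE start date only with first study treatment. For a missing day there are three branches: same month as the first dose (use the first-dose date), earlier month (use the last day of that month), and later month, which covers records whose known parts "are after the year and month of first study treatment, then the first day of the month will be assigned to the missing day". A reset to the stop date can only move an imputed start earlier.

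**Anchor.** SAP 2.4.1 ties the unqualified term to Visit 2: "The first date of study treatment is recorded on the Dose Administration (Visit 2) eCRF". SAP 2.1.1 defines a separate open-label date ("The date of first administration of study treatment in the open-label phase is defined as the first date" of open-label sacubitril/valsartan dosing), but 5.1.2 does not use it.

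**Phases.** In SAP 2.1.1 the double-blind interval for AEs is "Date of randomization (or date of first administration of study treatment, as appropriate) through the date of the Week 8 visit, inclusive". Open-label is "After the date of the Week 8 visit", with a projected date for patients who have no such visit. Those who "were lost to follow-up prior to or on their projected Week 8 visit date will be excluded from the open-label phase". The same holds for deaths and consent withdrawals up to then. The pooled phase includes "any assessment obtained in the open-label phase regardless of randomized treatment arm".

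**Use.** SAP 2.8.1.2: "All TEAEs will be summarized by study phase as defined in Section 2.1.1". Under protocol 3.1, open-label drug starts on the evening of the day after the Week 8 visit.

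**The concern.** Dating an event early is a cautious choice when the question is whether it is treatment-emergent. The phase tables ask a different question: was the patient still on randomized treatment, or already in the open-label period, when enalapril patients change drug? For that question early dating works in one direction only. It can carry an open-label event back into the double-blind phase and never the reverse.

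In both arms the double-blind column then covers more than 8 weeks. In an enalapril-randomized patient who had started open-label drug, an event that began on sacubitril/valsartan is shown under enalapril and is missing from the open-label and pooled sacubitril/valsartan tables. In the sacubitril/valsartan arm, the event changes phase but not drug.

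**Working it through.** **1. Logic.** Let W be the Week 8 visit date. The first of W's month is on or before W, and SAP 2.1.1 includes W in double-blind. So a day-missing AE recorded in W's month is always double-blind. If W fell in the first-dose month, the first-dose date would be imputed, which is also double-blind. A day-missing open-label AE in a later month is imputed to the first of that month, after W, and is placed correctly.

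*Example.* First dose 15 March 2017, Week 8 visit 9 May, true onset 20 May, recorded as May 2017. The imputed start is 1 May, so double-blind. A complete stop date of 25 May changes nothing.

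**2. Share moved.** The rule was run over all 1,461 first-dose dates from 2016 to 2019 (a span chosen only to cover the calendar), with onset on each of the 28 days after W.
- Onset days in W's month: 21,420 of 40,908 = 52.4%. All 21,420 went to double-blind. The share was the same with W 49, 55, 56 or 63 days after first dose.
- Hand check, 30-day month: sum of min(28, 30 − d) for d = 1 to 30 is 434; 434/(30 × 28) = 51.7%.
- Onset clustered early (exponential, mean 7 days, cut at 28): 77%. Mirror image, clustered late: 28%.
- Double-blind to open-label: 0%.
- If day and month are both missing, about 96% of open-label onsets go to double-blind.

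**3. Events moved.** Assume that 1% to 3% of AEs lack a day, with an even event rate over 57 double-blind days (first dose to W, 56 days later, inclusive) and 28 open-label days.
- 1,000 × (0.01 to 0.03) × 28/85 × 0.524 = 1.7 to 5.2 per 1,000 AEs.
- If 25% of patients never enter open-label (assumption), replace 28/85 by 21/78: 1.4 to 4.2.

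**4. Wrong drug.** Half the patients are on enalapril. About 6.6% of moved events fall on the day after W, mostly before the first open-label dose.
- Even onset: (1.7 to 5.2)/2 × 0.934 = 0.8 to 2.4 per 1,000.
- Early clustering (77% moved, 17% of those on the day after W): 1,000 × (0.01 to 0.03) × 28/85 × 0.770/2 × 0.830 = 1.1 to 3.2.
- Open-label event rate doubled (56/113 in place of 28/85), even onset: 1.2 to 3.6.
- Both together, upper end: 30 × 56/113 × 0.770/2 × 0.830 = 4.8.

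**5. Patients.** The tables count a patient once per category, so a moved event matters only if the patient has no double-blind event in that row. With L the mean double-blind events per patient in a row and q = (0.01 to 0.03) × 0.524, the gain per arm of 441 is 441 × exp(−L) × (1 − exp(−Lq/2)).
- Largest near L = 1: 441 × 0.368 × (0.0026 to 0.0078) = 0.4 to 1.3 patients.
- Same row, early clustering: 0.6 to 1.9. Doubled open-label rate: 0.8 to 2.5.
- Row with 10% double-blind incidence (L = 0.105): 0.1 to 0.3.

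**6. How ambiguous are these records?** In a 30-day month there are 465 double-blind onset days in W's month, summed over d and counting W itself, against 434 open-label days. So 434/899 = 48% of ambiguous day-missing AEs are truly open-label. If 25% of patients have no open-label time, it is 326/791 = 41%.

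**The case against.** **The effect is immaterial.** The partial-date rate is assumed, the tables are descriptive (protocol 9.5.3 rules out inferential safety analyses), and a 10% row gains 0.1 to 0.3 of 441 patients. Visits at most two weeks apart and data queries should keep partial dates few. Serious events are reported within 24 hours of the site learning of them. Hyperkalemia, creatinine, symptomatic hypotension and angioedema have their own data and summaries. All of this stands and limits the point to a minor one.

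**The present rule is a defensible convention.** It treats both arms alike and is right for about half of the ambiguous records. Anchoring on the open-label start instead would move about 94% of true double-blind onset days in the Week 8 month into open-label. This too stands, and it rules out a simple change of anchor. It does not make the rule suitable for a phase split when the record may already show the phase.

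**First study treatment might be read phase by phase.** SAP 5.1.2 names no phase, SAP 2.4.1 points to Visit 2, and the phase is unknown until the date is imputed. The single-anchor reading is much the likelier, though 5.1.2 does not spell it out. Nor does the SAP say in words that imputed dates set the phase, but it gives no other rule.

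**Stronger readings that the documents do not support.**
- A reader might infer that every moved enalapril event is shown under the wrong drug. Events in the 36-hour washout, or in patients who took no open-label drug, are misplaced by phase only.
- A reader might take 2.4 per 1,000 as a ceiling. It depends on even onset and equal rates; step 4 shows higher values.
- A reader might extend the point to medications, because SAP 5.1.3 repeats the rule and SAP 2.4.2 tabulates by phase. If a medication counts in every phase in which it was taken, early dating adds it to double-blind without removing it from open-label. The documents do not settle which applies.

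**Conclusion.** The point holds, as a minor one. The misplacement of day-missing open-label AEs recorded in the Week 8 month is certain from the text, given that imputed dates set the phase. Its size is not certain. About half of day-missing open-label AEs move with even onset (28% to 77% across the onset patterns tried). That is about 2 to 5 events per 1,000 AEs if 1% to 3% lack a day, with about 0.8 to 2.4 per 1,000 under the wrong drug. The latter rises to about 3.6 under early clustering or a doubled open-label rate, and that is not a strict maximum. In this trial it is probably a handful of events. Nothing here bears on the primary NT-proBNP analysis or the by-visit laboratory summaries.

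**What to change.** In SAP 5.1.2, add a check for AEs whose known start-date part fits both phases, in patients who enter the open-label phase:

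1. If a complete stop date is on or before the actual or projected Week 8 date, keep the present rule.
2. Otherwise, if the AE was first reported at a contact after the Week 8 visit, impute the day after that visit. For patients without the visit, use the first contact after the projected date, provided an earlier contact took place at or near that date, and impute the day after the projected date.
3. In all other cases keep the present rule.

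The day after the Week 8 date lies inside the recorded month whenever a day-missing record fits both phases. The first open-label dose may not, if dosing starts late.

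Protocol 7.1 does not list the contact of first report among the AE fields. If it is not captured, keep the present rule and add one sensitivity table that assigns the ambiguous events to open-label. The two tables bound each arm's own count. They do not bound the between-arm difference, whose extreme would place ambiguous events differently in the two arms.

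Extend the check to 5.1.3 only if medications are assigned to a phase by start date alone.

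The cost is SAP wording and minor programming before database lock, possibly one extra table, and no new data. The downside is that effort for what is probably a handful of events.

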5.1.3 Concomitant medication date imputation

The following algorithm should be used to estimate start dates for which only partial information is known:

- Missing day and month
 - If the year is the same as the year of first study treatment, then the day and month of the start date of treatment will be assigned to the missing fields.

Novartis	For business use only	Page 45
SAP Amendment 1		CLCZ696BUS01

- If the year is prior to the year of first study treatment, then December 31 will be assigned to the missing fields.
- If the year is after the year of first study treatment, then January 1 will be assigned to the missing fields.
- Missing month only
 - Treat day as missing and replace both month and day according to the above procedure.
- Missing day only
 - If the month and year are the same as the year and month of first study treatment, then the start date of treatment will be assigned to the missing day.
 - If the month and year are before the year and month of first study treatment, then the last day of the month will be assigned to the missing day.
 - If the month and year are after the year and month of first study treatment, then the first day of the month will be assigned to the missing day.

If the imputed start date result is after the stop date (and the stop date is complete), the imputed start date will be reset to the stop date.

The following algorithm should be used to estimate stop dates for which only partial information is known:

• Missing year

- Date left missing. Consider the medication to have been received at all periods after that period determined by the start date.

- Missing month
 - Impute 'December'.
- Missing day
 - Impute 'last date of that month'.

5.1.3.1 Prior therapies date imputation

The same imputation as concomitant medication will be used. See Section 5.1.3.

5.1.3.2 Post therapies date imputation

The same imputation as concomitant medication will be used. See Section 5.1.3.

5.2 AEs coding/grading

The coding team will code the AE terms using MedDRA terminology (v19.0 or later). If any terms are not coded, the data management team will issue queries to sites to update the AE term appropriately.

5.3 Laboratory parameters derivations

5.3.1 Laboratory grading

The collected laboratory values will be summarized by severity (low/normal/high) and not converted to Common Terminology Criteria for Adverse Events (CTCAE) grades.

5.3.2 Notable laboratory values

Hematology

RBC count	>50% increase, >20% decrease
Hemoglobin	>50% increase, >20% decrease
Hematocrit	>50% increase, >20% decrease
WBC count	>50% increase, >50% decrease
Platelet count	>75% increase, >50% decrease
Blood Chemistry	

ALT (SGPT)	>150% increase
AST (SGOT)	>150% increase
BUN	>50% increase
Creatinine	>50% increase
Total bilirubin	>100% increase
СРК	>300% increase
Alkaline phosphatase	>100% increase
Potassium	>20% increase, >20% decrease
Chloride	>10% increase, >10% decrease
Calcium	>10% increase, >10% decrease
Uric acid	>50% increase

5.4 Vital signs

5.4.1 Notable vital sign values

Systolic blood pressure	<90 mmHg and decrease of >20 mmHg from baseline	
	>140 mmHg and increase of >20 mmHg from baseline	
	>160 mmHg and increase of >20 mmHg from baseline	
	<90 mmHg	
	>140 mmHg	
	>160 mmHg	
	Decrease of >20 mmHg from baseline	
	Increase of >20 mmHg from baseline	
Diastolic blood pressure	<50 mmHg and decrease of >15 mmHg from baseline	
	>100 mmHg and increase of >15 mmHg from baseline	

Novartis SAP Amendment 1	For business use only	Page 47 CLCZ696BUS01
	<50 mmHg	
	>100 mmHg	
	Decrease of >15 mmHg from baseline	
	Increase of >15 mmHg from baseline	
Pulse	<50 bpm and decrease of >15 bpm from baseline	
	>120 bpm and increase of >15 bpm from baseli	ne
	<50 bmp	
	>120 bpm	
	Decrease of >15 bpm from baseline	
	Increase of >15 bpm from baseline	
Weight	>7% decrease; >7% increase	

